### **9.7.3 Selection of the Population to Describe and Compare Incidence of AESIs**

For the cohort study, exposure PS will be used to refine the initial matched comparator populations for use in analyses to describe and compare incidence of AESIs. This approach is proposed to improve exchangeability, reduce non-positivity, and control for confounding ([Webster-Clark et al 2021](#)). Propensity scores will be estimated separately within each database. The PS will serve as a within-database variable that summarises the confounding from a large set of variables. This advantage may be important in this study, given the low number of events for many of the study endpoints expected in the study population ([Austin 2014](#), [Cepeda et al 2003](#), [Webster-Clark et al 2021](#)).

#### **9.7.3.1 Selection of Covariates to Estimate Propensity Scores**

The strategy for selecting candidate covariates to estimate PS focuses on variables related to the probability of receiving the vaccine as well as those associated with the risk of one or more of the study outcomes. Candidate variables are listed in [Appendix C \(Annex Table 3\)](#). It is proposed to estimate only 1 PS for the analysis of all outcomes for each comparison. Using a single PS model to control for confounding in settings with more than one outcome, a generic outcome PS model, is preferred in terms of precision and bias. These generic outcome models include all covariates affecting any of the outcomes, while excluding covariates that only affect treatment ([Brookhart et al 2006](#), [Wyss et al 2013](#)).

The PS estimated in the full cohort has also been shown to be a valid approach for inference within subgroups given a minimum number of subjects and events. This one PS will serve to adjust for confounding in the analysis of all AESIs, including those AESIs that have specific exclusion criteria and to adjust for confounding in the subgroup analyses ([Girman et al 2014](#), [Rassen et al 2012](#)).

#### **9.7.3.2 Estimation of Propensity Scores**

Separate PSs will be estimated for each of the 3 comparisons conducted: AZD1222 cohort with concurrent unvaccinated comparator cohort, AZD1222 cohort with active comparator cohort, and AZD1222 cohort with historical comparator cohort.

Logistic regression models will be used to estimate PSs. From the fitted PS model, a PS will be estimated for each subject for each potential index date the subject was included in the model. Propensity score distributions will be produced for each cohort for each comparison.

#### **9.7.3.3 Selection of Cohorts for Comparative Analyses and Assessment of Balance**

After PSs have been estimated, using an approach that will be specified in the SAP, they will be used to refine the balance between study cohorts, which were initially matched, as applicable, on calendar date, age, sex, region, prior diagnosis of COVID-19, and status according to the 5 special populations. Whether all potential comparators, or only a sample, will be included will depend on the approach selected, as well as data governance rules and data management capabilities at each research partner, which are to be determined. Covariate balance will be assessed using the standardised differences and will be displayed graphically. If balance cannot be achieved for all important covariates, an option would be to refit the model to include interactions or higher-order terms to improve balance.

#### **9.7.3.4 Feasibility Assessment of Cohort Comparability for the Active Comparator Population**

The feasibility assessment of cohort comparability will be conducted in the pre-matching populations (ie, after applying inclusion criteria and prior to matching), for AZD1222 vaccinees with 2 consecutive doses of AZD1222) and active comparators cohort, also with 2 doses of mRNA vaccines.

The distribution of the baseline covariates used for matching will be described within each data source. Covariate balance will be assessed using the standardised mean differences and will be displayed graphically. Histograms detailing the overlap in age by calendar time between subjects in the AZD1222 cohort and subjects in the active comparator cohort will be provided, both overall and separately stratified by special population group. The denomination of calendar time will be defined in the SAP. Additionally, a logistic regression model will estimate propensity scores for receiving AZD1222 with the matching variables as covariates. Following the estimation of the propensity scores, the predictive ability of the model can be assessed using the area under the receiver operating characteristic (ROC) curve. A ROC curve plots the sensitivity against 1 minus the specificity of a model. Where our propensity score model is an excellent predictor of treatment (i.e.  $AUC > 0.8$ ; (Mandrekar 2010)), this suggests that the covariates are strong predictors of treatment and indicates fundamental differences between the AZD1222 cohort and the active comparator cohort. Large values of AUC of ROC curves indicate the importance of adjusting for all confounders (observed and unobserved) correctly to prevent unfair treatment comparisons. In the situation of large values of AUC, the suitability of the analysis with the active comparator will be reconsidered. Additionally, the examination of the effective sample size will be considered. Should we be able to proceed with the comparative analysis, the matching will be conducted as described in Section [9.2.1.1.3](#).

#### 9.7.4 Exclusions for Analysis of Specific AESIs

In general, the entire population identified in Section 9.7.3 will be included in the analysis of IRs, and with restrictions as appropriate for estimates of relative risk. However, in the analysis of specific AESIs, certain subjects who experienced the outcome in the recent past will be excluded from that analysis. The rationale for this approach is to be able to differentiate ongoing care for the historical event from a truly recurrent or incident event. Definition of the “recent past” (or “event-free interval”) will vary by outcome, and proposed specifications appear in Table 3. Some AESIs are chronic conditions, characterised by daily symptoms, that may not have discretely identifiable clinical recurrences, such as chronic fatigue syndrome or fibromyalgia. Subjects with a history of these conditions at baseline will be excluded from analysis of their incidence and relative risk. The SAP will also specify such conditions. Due to these exclusions, the exact composition of the analysis population may vary in the evaluation of different AESIs. The number of subjects excluded from each cohort for each analysis will be reported.

#### 9.7.5 Missing Data

Because the underlying data represent attended medical care, we generally assume that the absence of information of clinical events or prescriptions/dispensings indicates an absence of the condition or the treatment. Therefore, no missing data on diagnosis and medications are expected.

Missingness is only expected for some lifestyle or biometric data, such as smoking status or BMI in primary care electronic medical records. In the other data sources, these variables are not captured and will be defined based on proxies that do not have missing data (ie, use of smoking cessation drugs or diagnosis of obesity). In the main analysis, when describing a variable, subjects with missing values will be reported as a separate category.

The presence of missingness will be analysed. In the case of < 10% of missingness, a complete-case analysis is proposed for the main analysis. A complete-case analysis consists of performing the adjusted analyses described in the next subsections only among subjects with no missing values, under the assumption that data are missing completely at random. However, in the case of > 10% of missingness for key covariates, multiple imputation will be explored.

#### 9.7.6 Analysis of Incidence Rates

The analyses described below will address primary objective 3 and exploratory objective 1.

- For AESIs with **known risk windows** (those for which the end of the risk window is other than 180 or 365 days), crude IRs, and 95% CIs for each AESI will be estimated for the vaccinated cohort and the comparator cohorts. These analyses will combine person-time at risk after dose 1 and dose 2 (if it was received), using definitions of time at risk presented in Section 9.2.3.1. Exploratory analyses will report the IRs by specific dose.

For 2 specific AESIs, anaphylaxis and sudden death, since time to the event was not of interest, the prevalence proportions (PPs) and 95% CIs will be estimated.

- For AESIs with **unknown risk windows** (those with a risk window that ends at 180 or 365 days), cumulative incidence will be estimated using 1 – Kaplan-Meier survival curves starting at the index date. In addition, for AESIs with **unknown risk windows**, we will also describe the cumulative incidence over sequential time periods (eg, fortnights) to explore potential changes in risk over the follow-up period.
- In the primary analysis, IRs, PPs, and cumulative incidence of AESIs will be described for the AZD1222 cohort and for the 3 comparator cohorts (concurrent unvaccinated comparators, active comparators, and historical comparators) selected for comparative analyses (Section 9.7.3.3).
- For exploratory objective 1, in the AZD1222 matched cohort to active comparator cohort, the AESIs following a single dose of AZD1222 will be described.

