### 9.1.1 Retrospective Cohort Design

A retrospective cohort of exposed subjects will be selected. Subjects will enter the exposed cohort upon their first vaccination with AZD1222. Subjects in the AZD1222 cohort will be matched, as applicable, to 3 different comparator cohorts: concurrent unvaccinated subjects, active comparators (ie, subjects vaccinated with an mRNA vaccine against COVID-19), and historical comparators enrolled in the study data sources during the pre-pandemic period (ie, from 2017 to 2018). The AZD1222 cohort will be matched, as applicable, independently to the 3 different comparator cohorts on calendar date of vaccination, age, sex, region, prior COVID-19, and status according to each of the 5 special populations (Section 9.2.1.2). Propensity scores (PSs) will be used to address confounding, balancing multiple covariates such as comorbidities, markers of healthcare utilisation and comedication between the vaccinated and the different comparator cohorts (Austin 2014, Webster-Clark et al 2021). Relative risk will be the main measure of effect, which will be estimated using incidence rate ratios (IRRs), prevalence proportion ratios (PPRs), or hazard ratios (HRs), depending on the analysis and outcome. Absolute risk difference measures will include incidence rate differences, prevalence proportion differences (PPD), and  $1 - KM^2$  differences.

In the cohort study, the initial plan was to use concurrent, rather than historical, comparator (unvaccinated) subjects because they are at risk for COVID-19, and COVID-19 may function as an important covariable in the analyses of several of the safety endpoints. Moreover, both healthcare-seeking behaviours and healthcare delivery during the pandemic differ from those during the pre-pandemic era. The potential challenge with this approach is that during the pandemic, concurrent unvaccinated subjects in the comparator group may themselves become vaccinated over time. Results from Interim Reports 1 and 2 confirmed that the duration of follow-up among concurrent unvaccinated subjects was short (median, < 2 months in all data sources) and probably not long enough to evaluate AESIs with unknown risk window—(those with a risk window that ends at 180 or 365 days). Thus, additional comparators for whom the follow-up is expected to be longer were requested by the PRAC and have been added to the

---

[figure not shown]
 KM, Kaplan-Meier estimate.

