#### 9.2.3.1 Cohort Design: Follow-up

Follow-up will start on the index date and end on the earliest of the following possible follow-up termination dates:

- The end date of the study period.
- The subject's enrolment termination date in the health plan or system.
- The subject's date of death.
- For the specific evaluation of each AESI:
  - The date of the first diagnosis of a specific AESI recorded after the index date, during the study period. For composite outcomes, follow-up will be censored at the date of the first occurrence of any of the components.
  - For the evaluation of AESIs with **known risk windows** (ie, those for which the end of the risk window is other than 180 or 365 days), the date on which the defined risk window for the last dose ends (the last dose was dose 1 if only 1 dose was received and dose 2 if 2 or more doses were received).
    - For subjects who received 2 doses of AZD1222, or of an mRNA vaccine, and were not censored due to an AESI or other censoring criteria before the second dose, a second risk window will follow the second dose; and for concurrent unvaccinated comparators or historical comparator subjects, a corresponding second risk interval will also apply, mirroring the timing of the second risk interval for the matched vaccinee (Figure 4). As previously noted, the start and duration of the risk windows will be specific to each outcome, corresponding to the period when the biologic effect of a vaccine is hypothesised to increase the risk for the particular AESI (Section 9.1.2). If an AESI occurs during a gap between doses, this AESI will not be included as an event in the study, and as stated above, the follow-up will be censored at the time of the AESI.
    - This risk window applies to both the vaccinee and matched comparator subjects.

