### 9.7.7 Crude and Adjusted Measures of Association: Cohort Design

The analyses described below will address primary objective 4 and exploratory objectives 2.

- The analysis will compare subjects vaccinated with AZD1222 with the concurrent unvaccinated comparators and historical comparators to estimate the effect of receiving any dose (a first or a second), under the assumption that the effect of either dose is homogeneous. The effect of each individual dose on AESIs, will be estimated as prior vaccine exposure may “prime” the immune system.
- For outcomes that have **known risk windows**, we propose to estimate crude and adjusted IRRs and IR differences with 95% CIs using Poisson regression models. Specifically, the IRRs would be estimated using Poisson regression with robust estimation of the variance to account for individuals who may contribute person-time at different points to the exposed and unexposed cohorts (Zou 2004). For anaphylaxis and sudden death, crude and adjusted PPRs and PPDs with 95% CIs will be estimated using Poisson regression models with robust estimation of the variance to account for individuals who may contribute person-time to the exposed and unexposed cohorts at different timepoints.
- For outcomes **with unknown risk windows**, we propose estimating crude and adjusted relative risks and absolute risk differences. The relative risk (HRs) and 95% CI will be estimated using Cox regression models with robust estimation of the variance time-to-event analyses (Allison 2010). Using Cox regression models allows the flexibility to potentially adjust for time-dependant covariates, such as intercurrent COVID-19 infection.
- Adjustment for confounding will occur using PS, either through PS matching or by analytic methods involving stratification or weighting, which will be specified in the SAP. In the event that important covariates remain imbalanced after final selection of the cohorts for comparative analyses, additional approaches for confounding adjustment will be considered, including double-robust methods (ie, including the covariate in the outcome model as a separate term) or through analyses that restrict the population to subjects with more similar baseline characteristics (eg, subjects without substantial comorbidity).

The analysis described below will address exploratory objective 3

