### 9.7.10 Sensitivity Analyses

For each of the matched cohort populations (ie, AZD1222 cohort with concurrent unvaccinated comparator cohort, AZD1222 cohort with active comparator cohort, and AZD1222 cohort with historical comparator cohort), the following sensitivity analyses will be conducted analogously to the main analysis:

- The direct effect of vaccination with AZD1222 on the AESIs will be estimated, excluding subjects with prior COVID-19 diagnosis and thus censoring their follow-up at the occurrence of a COVID-19 diagnosis.
- The effect of partial censoring within matched pairs on the AESIs will be estimated by censoring both members of a matched pair when one member is censored.
- For thrombocytopaenia with bleeding, an alternative risk window of 1 to 28 days at the index date (instead of the 1 to 42 days in the primary analysis) will be assessed.
- For TTS; 3 alternative risk windows of 1 to 14 days, 1 to 21 days, and 1 to 28 days after the index date (instead of 1 to 42 days in the primary analysis) will be assessed.
- For TTS; an alternative definition of the outcome will include not only thrombocytopaenia with venous thromboembolisms but also thrombocytopaenia with AMI or stroke. The risk window between thrombocytopaenia and AMI or stroke will be the same as the one used for venous thromboembolism, ie, 10 days.
- For TTS; AESI cases will be restricted to confirmed cases (ie, excluding cases that could not be validated). The resulting positive predictive values (PPVs) will be used to correct the observed PPV from the main results. This analysis will be performed depending on the total number of outcomes that will be validated (as detailed in Section 9.3.2.1.1).
- In CPRD, a sensitivity analysis using hospital data to assess the AESIs will be performed at the time of the final analysis. However, depending on the duration of the lag time for hospital data at the time of the final analysis, the analysis using hospital data may be considered as the primary analysis.

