This study is potentially subject to **detection bias**, which can occur when knowledge of exposure leads to differential intensity of outcome ascertainment. A vaccinated individual may be more attuned to the possibility of an adverse reaction following vaccination and have a different threshold for seeking medical evaluation of symptoms than someone who is unvaccinated. Physicians who are aware of a subject’s vaccination status may also have a different threshold for evaluating nonspecific findings in the postvaccination period. We suspect that certain outcomes may be more subject to detection bias, particularly those with a more gradual onset or early symptoms that can be nonspecific, such as autoimmune thyroiditis. In contrast, someone with a new-onset seizure nearly always seeks prompt medical attention. Concerns that publicity about potential adverse effects may lead to differential ascertainment over time can be addressed through inspection of IRs in sequential periods during the study.

**Uncertainty about risk periods** may lead to misclassification and potential attenuation of risk estimates in the cohort design, particularly in the SCRI design. For AESIs with gradual onset, such as multiple sclerosis or peripheral neuropathies, the date of disease onset will likely precede the date of first recorded diagnosis; for events diagnosed shortly after vaccination, there is the possibility that the order of events (exposure/outcome) may actually be reversed. These concerns can be partially addressed through sensitivity analyses that introduce lag intervals. Approaches to address this limitation will be discussed in the SAP.

For AESIs with **known risk windows**, the main cohort analysis will pool risk estimates from risk windows after the first and second doses of AZD1222. Under the assumption that the

effect of a first or second dose in both populations is homogeneous, this pooling will increase study size and statistical precision. As this assumption is likely inaccurate, eg, because receiving a first dose sensitises the immune system to react against a second dose, the estimates of the main analysis could be biased. This factor may be especially important when evaluating immune-mediated AESIs, such as anaphylaxis. We will evaluate the IRs after each dose and report the relative effect measures separately.

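### The main known-window IRR against concurrent unvaccinated comparators pools both dose windows with no window term, so it can move away from 1 under no effect if background rates differ between the windows

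*Protocol*

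**What the plan says.** Section 9.7.6 covers incidence rates for known-window AESIs: "These analyses will combine person-time at risk after dose 1 and dose 2 (if it was received". Section 9.9.1 confirms that this is also the main comparative analysis: "the main cohort analysis will pool risk estimates from risk windows after the first and second doses of AZD1222". Section 9.7.7 gives the model, in which "the IRRs would be estimated using Poisson regression with robust estimation of the variance", and supports pooling "under the assumption that the effect of either dose is homogeneous". On confounding, leaving the choice of method to the SAP, it adds: "Adjustment for confounding will occur using PS, either through PS matching or by analytic methods involving stratification or weighting, which will be specified in the". None of these sections names a term for risk window or for calendar time at risk.

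For comparators, Section 9.2.3.1 provides that "a corresponding second risk interval will also apply, mirroring the timing of the second risk interval for the matched vaccinee". Section 9.1.1 reports from the interim analyses that follow-up of the concurrent unvaccinated "was short (median, < 2 months in all data sources". Section 9.5 expects a 3:1 ratio of vaccinated to concurrent unvaccinated person-time in the final analysis, although matching is 1:1. Section 7 gives a dose interval of 28 to 84 days.

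Two related analyses are planned. Sections 9.7.7 and 9.9.1 call for separate effects by dose. Section 9.7.10 includes a sensitivity analysis "by censoring both members of a matched pair when one member is censored".

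**The concern.** A two-dose vaccinee contributes equal time to the two windows. A comparator's mirrored second window opens weeks after index, when many comparators have already left. The pooled model therefore compares vaccinated time that is half early and half late with comparator time that is mostly early.

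Matching aligns calendar date at index only. A propensity score estimated at index cannot balance time accrued afterwards, whether it is used for matching, stratification or weighting. The defence offered for pooling is a homogeneous dose effect, and Section 9.9.1 discusses bias only if that fails. Changing background rates are a separate route to bias that stays open even when the dose effect is homogeneous. The protocol itself expects change over time: Section 9.9.1 refers to shifting infection patterns and care-seeking, and Section 9.1.1 to background rates altered by the pandemic.

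By a count of Table 3, the pooled IRR is the main estimate for 23 AESIs, setting aside anaphylaxis and sudden death, which use prevalence proportions. It serves primary objective 4. The stake is a shifted main estimate, in either direction, in a safety study.

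**Working it through.** **Inputs from the protocol.** 42-day windows, 84 days per two-dose vaccinee, and background rates per 100,000 PY of 2 (GBS), 38 (Bell's palsy) and 100 (VTE) (Section 9.5, Table 5); 3:1 person-time (Section 9.5); median comparator follow-up under 2 months (Section 9.1.1); dose gap 28 to 84 days (Section 7). Matched vaccinees (Table 4): 3,938,490 + 517,015 + 609,842 + 336,889 + 154,858 = 5,557,094. Gaps below 42 days make 42-day windows overlap, so gaps of 42 to 84 days are used.

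**Assumptions.** Exponential comparator exit, all vaccinees receiving two doses (as Table 5 assumes), and *k*, the background rate in the dose-2 window divided by that in the dose-1 window.

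**1. The plan's own figure.** For GBS with 5 million vaccinated at 3:1, vaccinated events a = 2/100,000 × 5,000,000 × 84/365.25 = 23.0 and comparator events b = 23.0/3 = 7.7. The probability that the upper limit is below 3 is Φ(ln 3/√(1/23.0 + 1/7.7) − 1.96) = 0.75, as stated. Table 5 therefore applies 3:1 to time inside the risk windows: 28 comparator days per 84 vaccinated days.

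**2. Comparator time by window.** With exit rate L and dose gap g, W1 = (1 − e^(−42L))/L, W2 = e^(−gL) × W1 and f = W2/(W1 + W2). L is set either by W1 + W2 = 28 (the 3:1 ratio) or by L = ln 2/median.

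**3. Pooled IRR under no effect.** IRR = (0.5 + 0.5k)/((1 − f) + f·k).

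| Exit pattern | Gap (days) | Reach dose-2 window | f | IRR, k = 0.7 | IRR, k = 1 | IRR, k = 1.5 |
|---|---|---|---|---|---|---|
| 3:1 | 84 | 11% | 0.097 | 0.88 | 1.00 | 1.19 |
| 3:1 | 42 | 24% | 0.196 | 0.90 | 1.00 | 1.14 |
| median 30 d | 77 | 17% | 0.144 | 0.89 | 1.00 | 1.17 |
| median 60 d | 77 | 41% | 0.291 | 0.93 | 1.00 | 1.09 |
| median 60 d | 42 | 62% | 0.381 | 0.96 | 1.00 | 1.05 |

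At k = 1.1 and a gap of 77 days, the two median-based patterns give only 1.02 to 1.035.

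The null rate difference is λ1 × (k − 1) × (0.5 − f), with λ1 the dose-1 window rate. Taking λ1 = 100 per 100,000 PY and k = 1.5, it is 100 × 0.5 × 0.403 = 20 per 100,000 PY at f = 0.097, and 100 × 0.5 × 0.119 = 6 at f = 0.381.

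**4. Against random error.** SE(log IRR) = √(1/e + 1/u), with e the expected vaccinated events and u = e/3.

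- VTE, all sources: e = 1,278, u = 426, SE = 0.056. A null IRR of 1.17 is ln 1.17/0.056 = 2.8 SE; 1.09 is 1.5 SE.
- VTE by source, null IRR 1.17: CPRD 2.4 SE, SIDIAP 0.93, VID 0.86, ARS Toscana 0.69, PHARMO 0.47.
- Bell's palsy, all sources, null IRR 1.09: 0.95 SE.
- GBS, all sources (u about 8.5), null IRR 1.17: 0.4 SE.

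These SEs ignore repeated comparators and weighting, which would usually widen them.

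**5. Stratified by window.** Within each window both groups have the same background rate, so each window-specific null IRR is 1. The Mantel-Haenszel combination (3:1, 84-day gap) is 1.00 at k = 0.5, 1 and 2.

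**6. Cost in precision.** With equal rates, information per pair is proportional to the sum over windows of V·C/(V + C), where V and C are vaccinated and comparator days. Pooled: 84 × 28/112 = 21.0. Stratified (3:1, 84-day gap, W1 = 25.3, W2 = 2.7): 42 × 25.3/67.3 + 42 × 2.7/44.7 = 18.3. The SE rises by √(21.0/18.3) = 1.07, about 7%.

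**The case against.** The strongest reply is that the protocol already plans the within-window comparison. Separate dose effects are to be estimated, and the comparators' dose-2 window mirrors the vaccinee's, so dose-specific IRRs are window-specific. Pair-censoring and a description of follow-up by matching covariates (Section 9.7.1) would also expose the imbalance. This is right as far as it goes, and the plan should not be read as blind to differential follow-up. But neither planned analysis is the main estimate, and no rule says which prevails if they disagree.

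Second, the SAP may add strata or time-varying covariates, and the Section 9.7.6 sentence concerns incidence rates. The SAP could indeed add a window term. The objection here is to the pooling rule that Section 9.9.1 states for the main analysis, and to a justification that does not cover background rates.

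Third, the rate ratio k has no source in the protocol. That stands, and it limits the claim. A reader might infer that the pooled IRR necessarily departs from 1 under no effect; it does not, since at k = 1 it is exactly 1 whatever the imbalance. A reader might also infer that the bias generally exceeds random error for common AESIs. That holds only in some scenarios, such as VTE pooled or in CPRD at the larger null IRRs. It does not hold for GBS, nor at 1.17 in the four smaller sources. Finally, that few comparators reach the dose-2 window is an inference; the models above give about 11% to 62%.

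**Conclusion.** The concern holds in conditional form and only for the comparison with concurrent unvaccinated subjects. The protocol's own follow-up and person-time figures imply comparator time weighted towards the dose-1 window, and nothing stated for the main model corrects it. Whether bias results, and in which direction, depends on how background rates change between the windows. The protocol acknowledges such change without quantifying it.

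The shares and null IRRs rest on exponential exit, two doses per vaccinee, 42-day windows, and illustrative k of 0.7 and 1.5. With dose 2 at day 77 and a median of 30 to 60 days, the null IRR is 1.09 to 1.17 or 0.89 to 0.93; the table's other rows widen this to 1.05 to 1.19 and 0.88 to 0.96. It is worth correcting because the change is simple and the main estimate for common AESIs could be affected. It gives no ground for expecting that the study's results will be wrong.

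**What to change.** In Section 9.7.7, stratify the main Poisson models for both the IRR and the rate difference by risk window (dose 1 or dose 2, mirrored in comparators). The main estimate then combines the within-window comparisons already planned as dose-specific effects. State in Sections 9.7.7 and 9.9.1 that pooling also requires like-for-like background rates, which the strata supply.

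Add calendar-period terms only for AESIs with enough events. At 3:1, GBS yields about 8.5 comparator events over all sources and fewer than 1 in each of the four smaller ones, so calendar-month terms within a database could not be fitted reliably.

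Report the dose-specific and pair-censored estimates beside the main one for each AESI.

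The cost is one split of person-time and one model term, with no new data. Some precision is lost where few comparator events fall in the dose-2 window: about 4% to 7% on the SE at 3:1 for gaps of 42 to 84 days under the model above. For the rarest AESIs the second stratum may hold no comparator events and contribute little.
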